#### 10.1.4.3 Evaluation of Best Overall Response

The best overall response is the best response recorded from the start of the treatment until disease progression/recurrence (taking as reference for progressive disease the smallest measurements recorded since the treatment started). The participant's best response assignment will depend on the achievement of both measurement and confirmation criteria.

#### For Patients with Measurable Disease (i.e., Target Disease)

Target Lesions	Non-Target Lesions	New Lesions	Overall Response	Best Overall Response for when Confirmation is Required:
CR	CR	No	CR	$\geq 4$ wks confirmation
CR	Non-CR/Non-PD	No	PR	$\geq 4$ wks confirmation
CR	Not evaluated	No	PR	
PR	Non-CR/Non-PD/Not evaluated	No	PR	
SD	Non-CR/Non-PD/Not evaluated	No	SD	Documented at least once $\geq 4$ wks from baseline
PD	Any	Yes or No	PD	No prior SD, PR or CR
Any	PD*	Yes or No	PD	
Any	Any	Yes	PD	
* In exceptional circumstances, unequivocal progression in non-target lesions may be accepted as disease progression.				
Note: Participants with a global deterioration of health status requiring discontinuation of treatment without objective evidence of disease progression at that time should be reported as " symptomatic deterioration ". Every effort should be made to document the objective progression even after discontinuation of treatment.				

CONFIDENTIAL

This document is confidential. Do not disclose or use except as authorized.

**For Patients with Non-Measurable Disease (i.e., Non-Target Disease)**

Non-Target Lesions	New Lesions	Overall Response
CR	No	CR
Non-CR/non-PD	No	NonCR/non-PD
Not all evaluated	No	Not evaluated
Unequivocal PD	Yes or No	PD
Any	Yes	PD
Non-CR/non-PD is preferred over stable disease for non-target disease since SD is increasingly used an endpoint for assessment of efficacy in some trials so to assign this category when no lesions can be measured is not advised.		

**10.1.5 Duration of Response**

Duration of overall response: The duration of overall response is measured from the time measurement criteria are met for CR or PR (whichever is first recorded) until the first date that recurrence or PD is objectively documented, taking as reference for PD the smallest measurements recorded since the treatment started.

Duration of overall complete response: The duration of overall CR is measured from the time measurement criteria are first met for CR until the first date that recurrent disease is objectively documented.

Duration of stable disease: Stable disease is measured from the start of the treatment until the criteria for progression are met, taking as reference the smallest measurements recorded since the treatment started.

**10.1.6 Progression-Free Survival**

Progression-Free Survival (PFS) is defined as the duration of time from start of treatment to time to progression event, including objective disease progression, clinical deterioration attributed to disease, or death.

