#### **4.3 Patient assignment and randomization procedure for second cohort**

Each subject who satisfies the eligibility criteria and is accepted for the study will be assigned a unique identification number. The subject number will be used to identify the subject throughout the study and will be entered on all study documents. Once the subject identification number has been assigned, a confirmation email will be sent to all site personnel.

For the Randomized Cohort, subjects will be randomized to each treatment arm (SGI-110+irinotecan or regorafenib/TAS-102) prior to treatment administration and should not exceed 1 week of the planned dose. The assignment will not be blinded. Randomization will be stratified by standard treatment (Regorafenib or TAS-102) and time from last irinotecan treatment (> 6 months or < 6 months) through a dynamic algorithm to maintain balance between the arms as much as possible. For those assigned to treatment arm with standard of care therapy will receive regorafenib (if previously received TAS-102) or TAS-102 (if previously received regorafenib). If they have never received either regorafenib or TAS-102, choice of therapy will be deferred to treating physician and patient.

This is an open-label study. There will be no blinding of treatment assignment.

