$\leq 1$ out of 6 at highest dose level below the maximally administered dose	This is generally the recommended phase 2 dose. At least 6 patients must be entered at the recommended phase 2 dose.

Toxicity will be evaluated using the NCI Common Terminology Criteria for Adverse Events Active Version. The frequency of toxicities per organ system will be tabulated using descriptive statistics. All patients who receive any amount of the study drug will be evaluable for toxicity.

### 5.1.3 Stage 2

The second stage of this study will be conducted as an open-label, randomized trial. As of December 2015, the maximally tolerated dose from the phase I trial was determined at level 1G:

- SGI-110 45mg/m^2 SC D 1-5
- Irinotecan 125mg/m^2 IV D 8 and 15

CONFIDENTIAL

This document is confidential. Do not disclose or use except as authorized.

- Mandatory growth factor support during cycle 1:
  - Filgrastim (or institutional equivalent) 5mcg/kg SC C1 D 9-14
  - Peg-filgrastim 6mg SC C1 D16
  - Additional growth factor support during Cycle 1 and subsequent cycles per clinician judgment

Ninety-six eligible subjects will be randomized in a 2:1 ratio to receive either (1) SGI-110+irinotecan combination treatment in 28-day cycles (n=64) or (2) regorafenib 160 mg QD days 1-21 in 28-day cycles or TAS-102 35mg/m^2 BID days 1-5 and 8-12 in 28-day cycles as per physician choice (n=32). Safety data will be reviewed at least on a quarterly basis by the SRC.

**As epigenetic agents may take many months to show their benefit as seen in MDS/AML studies, in both Stage 1 and Stage 2, subjects receiving SGI-110 + irinotecan may continue receiving their assigned treatment if their disease progresses based on RECIST criteria, version 1.1 if 1) the patient is clinically stable, 2) the patient is informed of their scan results and agrees to continue therapy, and 3) the patient provider agrees that remaining on study would be appropriate for the patient.**

Crossover to the SGI-110+irinotecan combination treatment arm of the study will be permitted for subjects in the regorafenib/TAS-102 arm after there is evidence of disease progression.

Response and PFS will be evaluated from images by the designated investigators at each site.

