### **5.7 Duration of Follow Up**

After removal from study, participants will be followed every three months or sooner until death, whichever occurs first. Participants removed from study for unacceptable adverse events will be followed until resolution or stabilization of the adverse event. Post-study case report forms must be completed at least every three months until death and will capture information including subsequent treatments, response to subsequent therapy, and survival.

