**Moving to Phase II Component:** Our hypothesis is that SGI-110 treatment will sensitize colon cancer patients to retreatment with irinotecan. Accordingly, it will be important to see that the dose of SGI-110 that is at the MTD does have pharmacodynamics effects at the tumor level. Patient tumor biopsies post-treatment will be analyzed by LINE assay for demethylation to assess for at least 10% demethylation from baseline in the tumor biopsies. We aim to see this level of demethylation in at least 60% of post-treatment biopsies as previously described in phase O studies.

**Phase II primary objective:** Evaluate the progression free survival (PFS) in patients receiving combination SGI-110 plus Irinotecan compared to standard of care treatment with regorafenib or TAS-102. Events are defined as disease progression or death from any cause. All patients treated

CONFIDENTIAL

This document is confidential. Do not disclose or use except as authorized.

on protocol will be included in the determination of PFS, regardless of treatment modification or discontinuation.

Epigenetic therapy may take several cycles to exert its maximal benefit, and preclinical data has demonstrated initial tumor growth is possible prior to tumor shrinkage. Patients on treatment with SGI-110 and IRI will be allowed to remain on study if their tumor progresses on RECIST 1.1 criteria if they are 1) clinically stable, 2) their provider feels it would be in their best interest, and 3) the patient is informed of scan results and consents to remain on treatment. In this circumstance, they will be reimaged on schedule after 2 further cycles. If this subsequent imaging confirms progressive disease, the date of the progression even will be dated to the first (initial) scan date that progression was first documented.

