### Analysis of secondary objectives:

1. The 4-month PFS will be compared between arms of the study using a one-sided, 0.05 alpha level, log-rank test.
2. All patients included in the study must be assessed for response to treatment, even if there are major protocol treatment deviations. Each patient will be assigned one of the following categories: 1) complete response, 2) partial response, 3) stable disease, 4) progressive disease, 5) early death from malignant disease, 6) early death from toxicity, 7) early death because of other cause, or 9) unknown (not assessable, insufficient data).  
All subjects in the study will be included in the main analysis of the response rate. Patients in response categories 4-9 should be considered to have a treatment failure (disease progression). Thus, an incorrect treatment schedule or drug administration does not result in exclusion from the analysis of the response rate. Response rate will be estimated overall and by treatment arm. A Fisher's Exact or chi square test will be use to compare response rates across treatment arms.
3. Standard life table methods will be used to analyze OS. Four month, 1-year and median survival will be reported, overall and by treatment arm. We acknowledge that OS assessment will be compromised with the cross-over design and will report as such.
4. Baseline global methylation will be categorized as high or low and OS Kaplan Meier curves plotted by category. The change in global methylation will be categorized as positive or negative and OS Kaplan Meier curves plotted by category. Similar analyses will be used for individual expression markers.

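### Primary PFS covers only treated patients, timed from first dose, so randomised never-starters leave the open-label comparison; restore them without separating the PFS clock from the scan schedule

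*Combined protocol and SAP*

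**What the plan says.** **Population and time origin**

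- Section 10.1.6: "Progression-Free Survival (PFS) is defined as the duration of time from start of treatment to time to progression event".
- Section 14.1, Phase II primary objective: the sentence that fixes the PFS population has treated patients as its subject and continues "on protocol will be included in the determination of PFS, regardless of treatment modification or discontinuation".
- Section 4.3: Phase II patients are randomised "prior to treatment administration and should not exceed 1 week of the planned dose", and assignment is not blinded.
- Section 4.1: if protocol therapy is not received after registration, the registration may be cancelled. Nothing is said about keeping such a patient in the analysis.
- Section 14.1, analysis of secondary objectives: "All subjects in the study will be included in the main analysis of the response rate".
- Section 5.7: three-monthly contacts until death, on forms that "will capture information including subsequent treatments, response to subsequent therapy, and survival".

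**Event definition**

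- Section 10.1.6 counts progression events "including objective disease progression, clinical deterioration attributed to disease, or death".
- Section 14.1: "Events are defined as disease progression or death from any cause".
- Section 5.1.3: "Response and PFS will be evaluated from images by the designated investigators at each site".
- Section 10.1.4.3 has deterioration without objective progression reported under its own label, and asks for objective progression to be documented even after treatment stops.

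**The concern.** The primary objective is a randomised comparison of PFS. A patient who is randomised and never dosed has no PFS start date and is outside the stated population. The clause on treatment modification or discontinuation protects patients who stop or change treatment, not those who never begin. No other section restores them, so the secondary response endpoint keeps the randomised groups intact and the primary endpoint does not.

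Because everyone knows the assignment, non-start can depend on the arm. If it also depends on prognosis, the treated groups are no longer comparable.

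The event wording is a separate matter. Two analysts could build different primary datasets from the same records when a patient deteriorates clinically and no scan shows progression.

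**Working it through.** **Inputs from the documents.** 64 v 32 patients; one-sided 0.05 log-rank; 24 months of accrual plus 24 of follow-up; control median PFS 1.9 months; HR 0.526; scans every 8 weeks; regorafenib median OS 6.4 months.

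**Assumed.** Exponential progression, no interim look, median 4.5 months from progression to death (6.4 - 1.9), and every non-start rate and prognosis.

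**The plan's own figures.** The exponential model gives control 4-month PFS of 0.5^(4/1.9) = 23.2% (plan: 23%). At HR 0.526 it gives 0.232^0.526 = 46.4% (plan: 46.5%). The stated 83% power does not reproduce from the stated one-sided 5%. With 96 events, Schoenfeld gives z = 0.6425 × √(96 × 2/3 × 1/3) - 1.645 = 1.32, or 90.7%. That is a separate question, and nothing below depends on it.

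**Step 1: hand check of selective loss.** Let the same share of each arm have hazard multiplier 0.5, and let only the controls among them fail to start.

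- 3 of 32: share 0.094. Apparent log HR is about 0.094 × ln 0.5 = -0.065. With nearly every patient an event, the SE is 1/√(64 × 29/93) = 0.224. The shift is 0.065/0.224 = 0.29, so type I error is Φ(-1.645 + 0.29) = 8.8%.
- 5 of 32: 0.156 × 0.693 = 0.108; SE 1/√(64 × 27/91) = 0.229; shift 0.47; Φ(-1.17) = 12.0%.
- Multiplier 2 reverses the sign: Φ(-1.94) = 2.7% and Φ(-2.12) = 1.7%.

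**Step 2: simulation under HR = 1, never-starters dropped** (8-week scans, 2,500 to 6,000 trials per cell, plus a continuous-time run of 10,000; ranges are across repeated runs where available). The log-rank test itself runs at roughly 5.5-6% in samples of this size and ratio.

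| Dropped | Hazard 0.5 | Hazard 1 | Hazard 2 |
|---|---|---|---|
| 1 control | 6.7% | 5.7% | 4.3% |
| 3 controls | 9.8-10.7% | 5.6-6.3% | 3.2-3.9% |
| 5 controls | 12.9-14.1% | 4.8-6.3% | 2.7-2.8% |
| 6 in Arm A only | 2.3% | 5.0-5.5% | 7.8-8.9% |
| 6 and 3 (same proportion) | 5.4-6.0% | 5.4-6.0% | 5.4-6.0% |

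**Step 3: never-starters kept in.** Imaged every 8 or 13 weeks, type I error is 4.6-6.6% in every case. With survival follow-up only, it is 0.4-1.6% for 3 or 5 controls and 11-15% for 6 in Arm A, so imaging is needed. These runs have no start delay and do not distinguish the two time origins. With 6 and 3 never-starters who gain nothing, power at HR 0.526 is 83.8% all-randomised against 85.5% treated-only (repeat run: 83.2% and 84.5%).

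**Step 4: the clock.** The calendars in Section 9 run on cycles, so scans follow treatment start. A median of 1.9 months is 8.26 weeks, so 1 - 0.5^(8/8.26) = 49% of controls progress by the first scan and are recorded almost together. If the clock starts at randomisation and one arm starts treatment later, that arm's block of events falls after the other's, and the log-rank test reads the order as effect. Type I error, two runs:

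| Mean extra delay | Longer in control | Longer in Arm A |
|---|---|---|
| 1 day | 3.0%, 3.4% | 8.4%, 9.9% |
| 3 days | 1.4%, 0.6% | 17.7%, 22% |

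The start-of-treatment clock stayed at roughly 4.6-8% in one run and 5.5-6.6% in the other. The documents give no delays; those used are assumptions that fit inside the one-week limit.

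**Step 5: event wording.** Assume an off-study scan 0-30 days after the clinical call that shows progression.

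| Patients called clinically | Calls count as events | RECIST-only events |
|---|---|---|
| 10% of controls only | 10.2% | 9.0% |
| 20% of controls, 10% of Arm A | 10.0% | 8.6% |
| 10% in both arms | 5.8% | 5.6% |
| Arm A only | 2.8% | 3.4% |

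The rules differ by at most 1.4 points. With no scan and calls in 10% of controls only, censoring at the call gives 2.6% (power 79%), and following to progression at the next 8-week date gives 5.4% (power 90%). With calls in Arm A only, these rules give 10.0% and 5.7%. Following to death only ranges from 1.9% to 14.6%.

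**The case against.** Three arguments favour the plan.

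**The loss may be negligible.** Section 4.3 keeps the gap from randomisation to dose short, and crossover after progression (Section 5.8) gives a control patient a reason to start. Non-selective or balanced loss does no harm. This stands and limits the size. A reader might infer that the trial's type I error is 10-14%. The documents do not support that: they give no non-start rate, those figures need one-arm loss of several better-prognosis patients, and other patterns push the error down.

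**The start-of-treatment clock has a merit.** It matches the scan calendar. This also stands. A reader might infer that PFS should simply be timed from randomisation at no cost. Step 4 shows otherwise: a one-day imbalance affecting everyone can approach the effect of losing three selected controls. The population and the clock are separate decisions.

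**The event wording may be shorthand.** Disease progression in Section 14.1 can be read broadly enough to include what Section 10.1.6 lists, so a flat contradiction is not shown. The off-study evaluation within 30 days of last dose (Section 9), the final-visit activities (Section 5.9) and Section 10.1.4.3 will often supply a scan. What remains is that no section says how PFS treats deterioration when no later scan exists.

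None of this gives never-starters a place in the primary analysis.

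**Conclusion.** The concern holds on the text. The primary PFS set, as defined, omits patients randomised but never dosed, and the cancellation rule in Section 4.1 leaves their status open. It does not itself say that they leave the analysis.

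The size is conditional on assumed rates: about 10% or 14% type I error for 3 or 5 better-prognosis controls lost (hazard 0.5), about 3% for worse-prognosis controls (hazard 2), and near 5.5-6% for non-selective or balanced loss. These rest on exponential progression rather than the plan's piecewise hazards; a run with gamma frailty gave a similar pattern (10.1% with 10% of controls lost, 12.6% with 20% of controls and 2% of Arm A).

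The plan should be changed because the protection is cheap, not because bias has been shown. The event wording is a reconciliation point. Settling it makes the dataset unambiguous; it does not remove bias from unequal unblinded clinical calls.

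**What to change.** 1. In Sections 10.1.6 and 14.1, make the primary PFS population all randomised patients, analysed as randomised.
2. In Section 4.1, state that cancelling a registration after randomisation does not remove the patient from the analysis.
3. Follow never-starters for survival and, where they consent, for progression using available imaging at the Section 5.7 contacts. Report by arm how many have no imaging.
4. Choose the clock and the scan schedule together. Either time PFS from randomisation and schedule Phase II scans in both arms every 8 weeks from randomisation, or leave scans on cycles, keep start of treatment as the origin for treated patients and use the randomisation date for never-starters.
5. Report the treated-only, start-of-treatment analysis as a sensitivity analysis.
6. Reconcile Sections 5.1.3, 10.1.4.3, 10.1.6 and 14.1 into one PFS event definition. State how deterioration with no later scan is handled, and report the alternative as a sensitivity analysis. Censoring at the clinical call should not be treated as neutral (Step 5).

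**Cost.** Wording in the sections named; a short follow-up line for the few never-starters, who have no cycle-based schedule; about 1-2 points of power from dilution (85.5 - 83.8 = 1.7; 84.5 - 83.2 = 1.3). If scans are timed from randomisation, the Phase II calendars change and scan dates move by up to about a week.

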**10.2 Other Response Parameters**

CEA will be followed on study monthly for exploratory purposes but will not be used for response assessment.

Additionally in the phase II portion of the study, all subjects will be asked to complete a quality of life assessment using the Functional Assessment of Cancer Therapy (FACT-C) questionnaire at the start of study Cycle 1 Day 1, Cycle 3 Day 1, every other cycle

CONFIDENTIAL

This document is confidential. Do not disclose or use except as authorized.

subsequently (i.e. Cycle 5 Day 1, Cycle 7 Day 1, etc), and at end of study/study withdrawal (optional).

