- Tumor biopsies in all phase 1 subjects on study. Additionally, tumor biopsies will be collected on a select number of subjects in phase 2. The following sites: SKCCC, VUMC, MSKCCC, and USC-Norris, will obtain biopsies on a total of 36 patients (distributed roughly evenly between the sites) for the first patients enrolled to the phase 2 if they have both biopsiable disease and are randomized to SGI-110 + Irinotecan. Optional biopsies will also be requested of patients with baseline research biopsies who remain on trial through Cycle 6-9.
- Radiologic response assessment.
- CEA
- Quality of Life evaluation at start of study using the FACT-C questionnaire (Phase II only).

### 5.2.2 Cycle 1, Day 1

In order for patients to be treated, evaluations must meet laboratory guidelines per the eligibility criteria

CONFIDENTIAL

This document is confidential. Do not disclose or use except as authorized.

### 5.2.3 Cycle 1 Day 8, 15 and Subsequent Cycles, Day 1, 8, 15

In order for patients to be treated, evaluations must meet the following criteria:

- ANC  $\geq$  1250 /mCL
- Platelet count  $\geq$  75,000 /cu mm
- Bilirubin  $\leq$  2 mg/dL
- Creatinine  $\leq$  2 mg/dL

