## 9 STUDY CALENDARS

Baseline evaluations are to be conducted within 2-week prior to start of protocol therapy. Scans must be done  $\leq 4$  weeks prior to the start of therapy. In the event that the participant's condition is deteriorating, laboratory evaluations should be repeated within 48 hours prior to initiation of the next cycle of therapy

All assessments must be performed prior to administration of any study medication. All study assessments and medications should be administered within  $\pm 3$  days of the protocol-specified date, unless otherwise noted.

CONFIDENTIAL

This document is confidential. Do not disclose or use except as authorized.

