**Phase II Portion**  
**Arm A – SGI-110 + Irinotecan**

	Pre-Study	C1 d1	C1 d8	C1 d9-14	C1 d15	C1 d22	C2 d1	C2 d8	C2 d15	C2 d22	C3 d1 b	C3 d8 b	C3 d15 b	C3 d22 b	Off Study e
SGI-110 Days 1-5 a		X					X				X				
Irinotecan a			X		X			X	X			X	X		
Growth factor support				X--- a											
Informed consent	X														
History	X														
QoL questionnaire		X									X i				X
Concurrent meds	X	X	X		X	X	X	X	X		X	X	X		X
Physical exam (Ht, Wt, BSA, VS) g	X	X					X				X				X
Performance Status	X	X					X				X				X
CBC w/diff, plts	X	X	X		X	X	X	X	X		X	X	X		X
Serum chemistry d	X	X	X		X	X	X	X	X		X	X	X		X
CEA	X	X					X				X				X
Urinalysis	X	X					X				X				X
ECG	X														
Adverse event evaluation			X-----X												X
Tumor measurements	X		Repeated every 8 weeks. Documentation (radiologic) must be provided for subjects removed from study for progressive disease.												X e
Radiologic evaluation	X		Radiologic measurements should be performed every 8 weeks												X e
Archival Tissue	X														
B-HCG	X f														
Tumor Biopsy	X h							X h -----X h							
Research Bloods		X	X		X	X	X	X	X		X		X		X

CONFIDENTIAL

This document is confidential. Do not disclose or use except as authorized.

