**Quality of Life Assessment:** Quality of life will be assessed with the Functional Assessment of Cancer Therapy (FACT-C) quality of life tool. An overall quality of life score for the domains: physical well-being, social/family well-being, emotional well-being, and functional well-being, as well as the colon cancer specific subscale score will be obtained at the start of the study (Cycle 1 Day 1), at the beginning of cycle three (Cycle 3 Day 1), every other cycle subsequently (i.e. Cycle 5 Day 1, Cycle 7 Day 1, etc), and at the off study visit for every patient. Scoring will follow guidelines provided by FACIT administration guidelines manual. The change in total score between pre-treatment and the start of cycle three will be compared between arms of the study with a t-test. Two subscale sums of the total score: the sum of physical and functional well-being,

CONFIDENTIAL

This document is confidential. Do not disclose or use except as authorized.

and the sum of social/family and emotional well-being, will be similarly analyzed. The change in the colon cancer specific domain will also be compared between arms of the study. We anticipate that we will have minimal missing data at the start of cycle 3 as this is the first time a patient could come off study for progression. At this time point, any missing data would be due to DLTs, SAE events, or voluntary withdrawal. In these cases, documentation of the reason for missing data and the QoL at the time of withdrawal will be obtained with the off study evaluation.

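### The baseline FACT-C for the quality-of-life comparison is taken after open-label randomisation; moving it ahead of randomisation is a cheap improvement of minor weight.

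*Combined protocol and SAP*

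**What the plan says.** **When the form is completed.** Section 10.2 gives the FACT-C "questionnaire at the start of study Cycle 1 Day 1, Cycle 3 Day 1, every other cycle". The Quality of Life paragraph of section 14.1 says the scores "will be obtained at the start of the study (Cycle 1 Day 1), at the beginning of cycle three (Cycle 3 Day 1", so it equates the start of the study with that day. In section 9, the "QoL questionnaire" row of the Arm A calendar and of both Arm B calendars (regorafenib and TAS-102) has its first mark under C1 d1 and none under Pre-Study.

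**When patients are randomised.** Section 4.3 places randomisation "prior to treatment administration and should not exceed 1 week of the planned dose. The assignment will not be blinded", and adds: "This is an open-label study. There will be no blinding of treatment assignment".

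**How the score is used.** Section 14.1: "The change in total score between pre-treatment and the start of cycle three will be compared between arms of the study with a t-test". Two pairs of subscales (physical plus functional, and social/family plus emotional) and the colon-specific domain are also compared between arms. No baseline covariate is mentioned.

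**Two related provisions.** Section 9 states: "All assessments must be performed prior to administration of any study medication". Section 5.2.1 includes in its screening list "Quality of Life evaluation at start of study using the FACT-C questionnaire (Phase II only", without saying whether this comes before or after allocation.

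**The concern.** A baseline for a randomised comparison should be fixed before allocation can influence it. Here two influences can reach the Day 1 form.

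- **Knowledge of the arm.** Control patients expect a marketed oral drug and may cross over only after progression. Arm A patients expect the investigational combination. FACT-C items on sadness, hope, nervousness and worry about worsening (Appendix D) could respond to that news.
- **The Arm A biopsy.** Sections 5.2.1 and 8.3.1 require a baseline core biopsy of 4-6 passes in the first 36 phase II patients with biopsiable disease who have been randomised to Arm A. As written, this falls between randomisation and dosing. FACT-C has a seven-day recall period and asks about pain, so the Day 1 form can pick up a procedure that one arm alone undergoes.

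At stake is the interpretation of a prespecified between-arm test. An allocation-driven difference at baseline is subtracted from the change score and can look like a treatment effect, or hide one. Adjusting for the Day 1 score would not cure this, because the covariate would itself be affected by allocation.

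**Working it through.** The documents give no power, SD, target difference or sidedness for FACT-C, so there is no planned figure to reproduce. The check has two parts.

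**1. Order of events**

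| Step | Timing | Source |
|---|---|---|
| Screening | within 14 days before treatment | 5.2.1 |
| Randomisation, unblinded | before treatment, at most 1 week before the planned dose | 4.3 |
| Arm A-only baseline biopsy | after assignment to Arm A, before dosing | 5.2.1, 8.3.1 |
| First FACT-C | Cycle 1 Day 1 | 10.2, 14.1, three calendars |
| First dose | after that day's assessments | 9 |
| Arm A second biopsy | C2D8 to C2D15 | 8.3.1 |
| FACT-C for the comparison | Cycle 3 Day 1 | 14.1 |

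The first FACT-C is before treatment but after randomisation. Up to 36 of the 64 Arm A patients (36/64 = 56%) may have the baseline biopsy. With 28-day cycles, the second biopsy falls 14 to 21 days before Cycle 3 Day 1, outside the seven-day recall, so on schedule it does not offset the first.

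**2. Effect on the contrast**

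Let s be the allocation-driven difference (Arm A minus Arm B) in the Day 1 score, and p the fraction of it still present at Cycle 3 Day 1.

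- Contrast from the Day 1 baseline = contrast from a pre-randomisation baseline - s. This holds whatever p is.
- With no true quality-of-life effect, the Day 1 contrast has expectation ps - s = -(1 - p)s. From a pre-randomisation baseline it is ps.

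Illustration. Section 5.1.3 gives 64 and 32 patients. Assumed, not in the documents: SD of change 12-18 points, s = 2-4 points in absolute size, two-sided 5% test, complete data, normal approximation.

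- SE = SD x sqrt(1/64 + 1/32) = 0.2165 x SD, which is 2.60 at SD 12 and 3.90 at SD 18.
- z = (1 - p)s / SE. Rejection rate = Φ(z - 1.96) + Φ(-z - 1.96).

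| Persistence p | z at s = 2, SD 18 | z at s = 4, SD 12 | Rejection rate, no true effect |
|---|---|---|---|
| 0 | 2/3.90 = 0.51 | 4/2.60 = 1.54 | 8.1% to 33.7% |
| 0.5 | 0.26 | 0.77 | 5.8% to 12.0% |
| 1 | 0 | 0 | 5.0% |

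In SD units with p = 0, a shift of 0.1, 0.2 or 0.3 SD gives 7.5%, 15.2% or 28.3%. With about 20% missing (51 and 26 patients, also assumed) these become 7.0%, 13.2% and 23.8%.

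**The case against.** **Persistence.** The strongest objection is that the trial stays open label, so patients still know their arm at Cycle 3. A reader might infer from the 8% to 34% range that the planned test has that error rate. The documents do not support this: they give no SD or shift, and the range also needs the effect to have gone by Cycle 3 Day 1. If it persists in full, it cancels in the change score. This objection stands.

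**The fix has the mirror-image limit.** A reader might also infer that an earlier baseline restores the nominal 5%. From a pre-randomisation baseline the expected contrast is ps, so any expectation effect still present at Cycle 3 then enters in full. This stands too. The case for moving the form is that it gives a baseline allocation cannot touch, not that it gives an unbiased patient-reported outcome. The persistence argument has less force for the biopsy, whose discomfort has less reason to last to Cycle 3; that is a judgement, not a stated fact.

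**Screening list.** Section 5.2.1 could let a site collect the form before randomisation. This stands only as a wording inconsistency. The entry says start of study, which section 14.1 defines as Cycle 1 Day 1. The screening window is anchored to dosing, and the same list contains a procedure limited to patients already randomised to Arm A.

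**Knowledge of the arm.** No section says when patients are told, so knowledge by Day 1 is an inference. It is a strong one, given the Arm A-only biopsy and the patient's part in choosing the control drug where neither has been used.

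**Dilution.** Where randomisation is less than a week before Day 1, part of the recall period precedes allocation. The items most open to expectation lie in the six-item emotional domain, so the physical/functional and colon-specific comparisons are less exposed to that route, though biopsy pain falls in the physical domain.

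**Conclusion.** The timing finding is firm: the baseline of the planned FACT-C change score is a post-randomisation measurement in an open-label trial. That it can be influenced by allocation follows from the Arm A-only biopsy as written and, very probably, from knowledge of the arm. A Day 1 shift of s moves the contrast by -s relative to a pre-randomisation baseline.

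The size and net direction of any shift are unknown. The 8% to 34% range is conditional on every assumption listed above, including no persistence, and is not an estimate for this trial.

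The weight is minor. Quality of life is not among the phase II objectives in sections 1.2, 1.3 or 14.1. A reader might infer damage to the main result; there is none, because PFS, its power and the futility rule do not use this score. Nor is the baseline taken after treatment, since section 9 puts assessments ahead of study medication. This is a cheap improvement.

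**What to change.** - In 5.2.1, 10.2, 14.1 and the three phase II calendars, require the baseline FACT-C at the Pre-Study visit, after consent and before randomisation.
- In 14.1, define the change to Cycle 3 Day 1 from that form. A Cycle 1 Day 1 form may be kept as descriptive only.
- State in 14.1 that open-label reporting bias at later visits remains and that the comparison should be read accordingly.

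The cost is a wording and calendar amendment that moves one form to an existing visit and brings 5.2.1 into line with the calendars. The baseline becomes slightly earlier (up to 14 days before dosing under the screening window), and a few screen failures will complete a form. The sample size and the PFS analysis do not change. The change helps only patients not yet randomised, because a pre-allocation score cannot be recovered afterwards.
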